### **Device Deficiencies**

### **Serious Adverse Events (SAE)**

A Serious Adverse Event (SAE) is any AE that leads to any of the following:

- Death
- A serious deterioration in the health of the patient or the patient's partner by one or more of the following:
  - A life-threatening illness or injury, or
  - A permanent impairment of a body structure or a body function including chronic diseases, or
  - In-patient or prolongation of hospitalization, or
  - Medical or surgical intervention to prevent a life-threatening illness or injury, or permanent impairment to a body structure or body function
- Foetal distress, foetal death, a congenital abnormality, or birth defect including physical or mental impairment

*Note: In this study, planned hospitalization for a pre-existing condition, or procedure required by the protocol without serious deterioration in health will not be considered an SAE. SAEs will be reported to the Institutional Review Board and other required authorities within the required timeframe.*

### **Serious Adverse Device Effect (SADE)**

An ADE which results in any of the consequences as characterized in an SAE.

### **Serious Health Threat**

Signal from any AE or device deficiency that indicates an imminent risk of death or a serious deterioration in the health in patients, users or other persons, and that requires prompt remedial action for other patients, users or other persons. A device deficiency is the inadequacy of a medical device with respect to its identity, quality, durability, reliability, usability, safety or performance.

### **Unanticipated Serious Adverse Device Effect (USADE)**

A SADE which by its nature, incidence, severity or outcome has not been identified in the current risk assessment. In some regions, this may be referred to as an Unanticipated Adverse Device Effect.

AEs/ADEs will be collected from the signing of the ICF at screening (Visit 1) until the end of the investigation. Any AEs that are unresolved at the patient's last AE assessment during the investigation (i.e. at the patient's final investigation visit) are to be followed up by the PI for as long as medically indicated, but without further recording in the eCRF. FMD retains the right to request additional information for any patient and/or their female partner with ongoing AE(s)/SAE(s) at the end of the investigation, if judged necessary.

All AEs/ADEs will be recorded in the patient's paper diary and entered into the eCRF after review by the PI or suitable qualified designee (e.g. sub-investigators) at the next investigation visit. The details to be recorded are:

- The date of the AE/ADE onset and its resolution
- Treatment (if any)
- Seriousness
- Relationship to the investigational device or control and the related procedure

Any SAE/SADE/USADE will be notified by the PI or designee to the IRB and other authorities as per local regulations and requirements.

### **Concomitant Treatment**

The use of any concomitant treatment will be monitored throughout the study from the point of signing the ICF at Screening Visit (Visit 1) until the final study visit. The site will ask the patient about any concomitant treatment the patient is taking or any changes in concomitant treatment at each of the study visits.

Patients are not permitted to take other forms of ectogenic treatment during their participation in the study. Ectogenic treatments may include PDE5i inhibitors such as sildenafil citrate, vardenafil and tadalafil or mechanical devices used to treat erectile dysfunction.

#### **Central/Local Laboratories**

Analysis of serum PSA and hormonal (testosterone) assessment will be performed by Mass General Brigham central clinical laboratory or another certified laboratory (if the patient prefers).

### **7. Risks and Discomforts**

#### **Anticipated Adverse Events Associated with MED3000 topical gel:**

- Penile pain/discomfort
- Headache

#### **Adverse Events Associated with Blood Draws**

- Infection at blood sampling site
- Pain at blood sampling site
- Hematoma or thrombus
- Extensive bleeding
- Nerve Damage
- Vasovagal reaction Syncope, fainting
- Allergic Reaction

Of note, in regard to patients status-post radical prostatectomy for prostate cancer, approximately 20-40% of patients with clinically localized prostate cancer may present tumor biochemical recurrence after radical prostatectomy. There is no anticipated risk of biochemical recurrence with MED3000 topical gel.

All SAEs will be recorded and reported to IRB as required by their regulations.

### **8. Benefits**

Patients may not directly benefit from taking part in this research study. Other men with post-radical prostatectomy erectile dysfunction and their female partners may benefit in the future from what we learn in this study.

Patients may benefit from improvements in erectile function and quality of life.

### **9. Statistical Analysis**

#### ***Sample size calculation***

It is planned to enrol and treat approximately 20 patients for a 12-week treatment duration. There is no formal sample size calculation performed. This is an exploratory study for treatment of novel patient population without precedent.

### ***Statistical analysis***

Baseline characteristics of the trial participants will be summarized using the following baseline data. Mean, median, minimum, maximum and standard deviation or proportion (as appropriate) will be reported.

- Age
- Baseline comorbidities
- BMI
- Baseline IIEF/ SEAR/EPIC (+climacturia question) (following 4 week screening period)
- 24 hour pad weight
- 24 hour pad number usage
- Stretched penile length
- Prostate cancer stage (surgically-verified)

Full Analysis Set: Patients who received at least one dose MED3000 topical gel treatment.

Per-protocol Analysis Set: Patients who meet the inclusion/exclusion criteria and who have completed all the treatment and follow-up sessions up to the 12-week visit.

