***International Index for Erectile Function (IIEF) questionnaire***

The IIEF was developed and validated in 1996–1997 as part of the sildenafil clinical study program and in 1999, the IIEF was recommended by the first International Consultation on Erectile Dysfunction as the primary effectiveness endpoint of choice for clinical studies in ED. After years of use, the IIEF is considered the gold standard self-report questionnaire for measuring EF. The IIEF has been validated, is widely used in numerous countries, and has demonstrated specificity for detecting treatment-related changes in EF. The IIEF consists of 15 questions divided into five domains of sexual function: EF (6 questions), orgasmic function (2 questions), sexual desire, (2 questions), intercourse satisfaction (3 questions) and overall satisfaction (2 questions). A score of 0 to 5 is awarded to each of the 15 questions. Higher scores indicate better sexual function. The IIEF-EF domain, a subset of the IIEF measuring erection function, is commonly used as the primary endpoint in clinical trials and comprises Questions 1–5 and 15 of the IIEF. The questionnaire is completed by a patient's recollection of the effects that his erection problems have had on his sex life over the previous 4 weeks.

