site at Visit 5 Adverse events. Protocol compliance will be assessed by questioning the patient about their use of MED3000 and the number of unused tubes of MED3000 available. Patients will be asked about any changes to their concomitant medication and any new or changes to AEs (including their partner). Additionally, patients will be asked whether the patient or partner predominantly applied the gel to the glans penis prior to sexual intercourse.

Visit 4 (phone -Week 8 ( $\pm$  1 week)): Patients will be asked to complete the IIEF, EPIC, climacturia and SEAR questionnaires. The patient will bring the completed questionnaires to the site at Visit 5. Protocol compliance will be assessed by questioning the patient about their use of MED3000 and the number of unused tubes of MED3000 available. Patients will be asked about any changes to their concomitant medication and any new or changes to AEs (including their partner). Additionally, patients will be asked whether the patient or partner predominantly applied the gel to the glans penis prior to sexual intercourse.

Visit 5 (on-site -Week 12 ( $\pm$  1 week)): Patients have PSA serum samples taken and have a genital examination. Patients will also complete the IIEF, EPIC, climacturia and SEAR questionnaires. An assessment of the stretched flaccid penile length will be performed, heart rate and blood pressure will be measured. AEs, changes in concomitant treatment, and protocol compliance and a genital assessment will be assessed. The patient will return all used MED3000 tubes and unused MED3000 treatment at this visit and full verification of MED3000 usage compliance determined. The site will also perform an assessment of the patient's 24 hour pad weight and the number of pads used. Additionally, patients will be asked whether the patient or partner predominantly applied the gel to the glans penis prior to sexual intercourse.

Follow-up Visit 6 (phone-7 day post-study treatment, ( $\pm$  2 days)): Patients will provide details about ongoing or new adverse events and any new concomitant treatment. Usage of erectogenic aids will also be recorded. Patient will be instructed to continue with his primary urologist for PSA monitoring per standard of care.

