### **Analysis of Primary Efficacy Endpoint**

The primary efficacy assessment is the mean change in IIEF-EF from baseline (post 4-week washout) at 12 weeks. The observed primary efficacy assessment will be compared to the MCID of 4.

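### IIEF-EF scores obtained with prohibited erectogenic aids stay in both analysis sets, and no sensitivity analysis would show their effect on the mean compared with 4

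*Combined protocol and SAP*

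**What the plan says.** The ban appears twice. Section 3 (General Description of Study Design) allows no other aid in the treatment period, and Section 6 (Concomitant Treatment) states: "Patients are not permitted to take other forms of ectogenic treatment during their participation in the study". The latter section counts mechanical devices as well as drugs.

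The endpoint is stated in Section 9: "The primary efficacy assessment is the mean change in IIEF-EF from baseline (post 4-week washout) at 12 weeks". Then: "The observed primary efficacy assessment will be compared to the MCID of 4". Section 3 describes the IIEF as completed from the patient's "recollection of the effects that his erection problems have had on his sex life over the previous 4 weeks".

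Section 9 defines two sets. The Full Analysis Set is everyone who received at least one dose. The Per-protocol Set is "Patients who meet the inclusion/exclusion criteria and who have completed all the treatment and follow-up sessions up to the 12-week visit". Neither refers to other aids or to protocol deviations. Section 9 has no rule for scores obtained with an aid and no sensitivity analysis, and it does not impute missing data.

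On collection, the Concomitant Treatment section has the site ask about concomitant treatment at every visit. In the visit descriptions, aids are named only at Visit 6: "Usage of erectogenic aids will also be recorded".

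**The concern.** The aim is to learn what the gel does by itself, which is why the protocol has a washout and a ban. If a man returns to a PDE5 inhibitor, a vacuum device or injections in weeks 9-12, his week-12 score reflects that aid as well as the gel. There is no control arm to absorb the effect, and with about 20 men each one carries 5% of the mean. Section 3 itself expects that many men will have tried other aids by this time after surgery, so the situation is foreseeable.

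At stake is the second primary objective, a mean change of at least 4. As written, a mean on either side of 4 could owe part of its position to prohibited aids, and a reader of the planned output could not tell.

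**Working it through.** **Step 1. Does any rule remove or flag such a score?**

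- Full Analysis Set: one dose is enough. The score stays.
- Per-protocol Set, eligibility part: male inclusion criterion 11 asks for willingness to refrain. That is a state at entry, and a man who later uses an aid still met it.
- Per-protocol Set, completion part: it refers to treatment sessions, which an on-demand home gel does not have. Read as attendance, it says nothing about aids.
- Withdrawal Criteria: aid use is not listed. Insufficient cooperation may lead to dismissal, but that is discretionary and does not say how scores are counted.
- Deviations from the Protocol: deviations are logged and reviewed for risk and trend, with no link to an analysis set.

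The Per-protocol rule, followed exactly, therefore keeps the men who broke the ban.

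**Step 2. Can the questionnaire separate the sources?** No. The IIEF in Appendix 1 asks about sexual activity and intercourse over the past 4 weeks. No item is limited to gel-assisted attempts.

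**Step 3. Direction.** Change = week-12 score − baseline score. Aid use in the week-12 recall period raises the first term and so the change. Aid use in the recall period of the Visit 2 baseline raises the second term and lowers the change.

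**Step 4. Size.** The plan has no figure to reproduce: "There is no formal sample size calculation performed". The only input from the documents is n: "It is planned to enrol and treat approximately 20 patients for a 12-week treatment duration". The values of k (men using an aid) and d (points that the aid adds) are assumptions.

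Shift in mean = k × d / n, upward for week 12 and downward for baseline:

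| k | d | Shift at n = 20 | Share of 4 |
|---|---|---|---|
| 2 | 6 | 12/20 = 0.6 | 15% |
| 3 | 8 | 24/20 = 1.2 | 30% |

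For scale, assume an aid-free mean of 3, SD 7, a standard error of 7/√20 = 1.57 and a normal approximation. The chance of an observed mean of 4 or more is then 26% with no aid use, 42% with 2 men at +7 (shift 0.7) and 50% with 2 men at +10 (shift 1.0). With SD 5 the three figures are 19%, 39% and 50%; with SD 9 they are 31%, 44% and 50%.

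**Step 5. What different ways of handling would report.** Take 3 of 20 men with an aid adding 8 points, and an aid-free mean of 3.0 over all 20 (sum 60). Case A: these 3 men gain nothing from the gel. Case B: they gain 3 points each, like everyone else.

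| Handling | Case A | Case B |
|---|---|---|
| As observed | (60 + 24)/20 = 4.2 | (60 + 24)/20 = 4.2 |
| Men excluded | 60/17 = 3.53 | 51/17 = 3.0 |
| Set to zero change | 60/20 = 3.0 | 51/20 = 2.55 |

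Exclusion overstates the gel if the aid users are poor gel responders. Zero change is right in Case A and too low in Case B, so it is a conservative value.

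**The case against.** The strongest reply is that this is an exploratory pilot, that the comparison with 4 carries no formal decision rule, and that chance error is larger than the shifts shown. At n = 20 the 95% confidence interval half-width is 2.3, 3.3 and 4.2 points for assumed SDs of 5, 7 and 9, against shifts of 0.6 and 1.2. Inclusion criterion 5 also selects men with erectile dysfunction despite aids, which may limit both d and the incentive to return to an aid. These points stand as limits on size. They do not supply the missing rule: an interval shows sampling error, not a displacement of its centre, and the protocol itself makes 4 the target.

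Three stronger readings are tempting, and the documents do not support them.

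- A reader might infer that aid use goes unrecorded until after the last described IIEF. It does not. Concomitant treatment is asked about at every visit, in a section that names mechanical devices; Visit 5 covers concomitant treatment and protocol compliance; and Section 3 lists use of other aids as a study assessment. Efficacy is analysed only after all follow-up visits, so the Visit 6 answers are available too. What is lacking is an aid-specific, dated question at Visits 2-5.
- A reader might infer that the bias can only favour the gel. Step 3 shows that use in the baseline window works the other way.
- A reader might want the Per-protocol Set to require the 4 instructed gel-assisted attempts in weeks 9-12. That selects on behaviour after baseline. Men who gain little may stop using the gel, and removing them could itself raise the Per-protocol mean.

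**Conclusion.** The concern holds as a gap in the analysis rule. The protocol prohibits other aids, yet both analysis sets keep IIEF-EF scores obtained with them, and no planned analysis would reveal the effect. In a single-arm trial of about 20 men, use by two or three of them in weeks 9-12 could add roughly 0.6 to 1.2 points to the mean, or 15% to 30% of the benchmark. Use in the baseline window would subtract by the same formula.

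These sizes rest on assumed k and d and on 20 evaluable men. The documents give neither the frequency of prohibited use nor the gain from it, so the net effect could be nil. The collection gap is minor. The point deserves correction before data are seen, because with so few men a rule chosen afterwards could itself decide on which side of 4 the mean falls.

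**What to change.** 1. **Collection.** Within the concomitant-treatment question already asked at Visits 2-5, name erectogenic drugs and devices, and record dates of use over the IIEF recall period.
2. **Per-protocol Set.** Add the condition that no other erectogenic aid was used in the 4-week recall period of the baseline or the week-12 IIEF. Replace the undefined reference to treatment sessions with completion of visits to week 12. Do not add a minimum number of gel-assisted attempts.
3. **Sensitivity mean.** Beside the as-observed Full Analysis Set mean, report one in which any week-12 score with aid use in its recall period is set to zero change. Label it as conservative, and give the reason for not simply excluding these men (they may be the poor gel responders). Compare both means with 4.

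This changes how scores are recorded and counted, not how patients are managed. The cost is a sharper wording of one question at contacts already planned and a few lines in Section 9. The downside is a slightly smaller Per-protocol Set and possibly a less favourable mean.

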### **Analysis of Primary Efficacy Endpoint**

The primary efficacy assessment is the mean change in IIEF-EF from baseline (post 4-week washout) at 12 weeks. The observed primary efficacy assessment will be compared to the MCID of 4.

### **Analysis of Secondary and Safety Endpoints**

The secondary assessments are:

- Mean change from baseline in all domains of the IIEF at 4, 8 and 12 weeks, besides the IIEF-EF at 12 weeks.
- Mean change from baseline in SEAR, EPIC at 4, 8 and 12 weeks
- Mean change from baseline in stretched flaccid penile length at 12 weeks
- Proportion of patients on penile injection therapy or penile implant at 12 months follow-up
- Mean change in 24 hour pad weight and 24 hour pad number usage at 12 weeks
- Serum PSA indicative of biochemical recurrence
- Proportion of patients who experienced treatment-related adverse events

Continuous variables: Estimates of mean changes from baseline, along with 95% confidence intervals, will be produced. The change from baseline in endpoints within the group will be analysed by one-sample t-tests with a two-sided significance threshold of  $p=0.05$ , testing the null hypotheses of mean change from baseline equal to zero. Covariates / sub-groups may also be evaluated such as age and comorbidities.

Discrete variables: Estimates of proportions, along with 95% confidence intervals, will be produced.

Any missing, impossible (inconsistent with human life) or inconsistent recordings in the Case Report Forms will be referred back to the Principal Investigator and documented for each individual patient before clean file status is declared. Missing data will not be imputed.

Data will be analyzed with Microsoft Excel, Graphpad Prism 7, or equivalent statistics software. Efficacy endpoints will be analysed after the last patient has completed all follow up visits.

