### **3. General Description of Study Design**

This is an open-label, non-randomized, single-arm trial. Patients with no evidence of prostate cancer biochemical recurrence (Prostate specific antigen [PSA] undetectable) with mild to severe post-radical prostatectomy erectile dysfunction based on IIEF-EF criteria will be enrolled. Patients will washout from use of prior erectogenic regimens for at least four weeks in order to standardize the cohort and establish a symptomatic baseline. By the 1.5 to 4 year point after surgery, many men may have pursued other erectogenic aids. Patients will be instructed to cease all erectogenic aids for at least 4 consecutive weeks prior to commencing intervention. Aids may include phosphodiesterase 5 inhibitors, vacuum erection device, intraurethral suppository, or intracavernosal injection therapy. During the 4-week Screening Period, patients will be advised to attempt at least 4 sexual intercourse attempts. IIEF-EF will be assessed at the end of this period to assess candidacy for trial and assess baseline status.

All eligible enrolled patients will receive treatment with MED3000 topical gel and use on demand for up to 12-weeks. Patients will be assessed at 4 weeks, 8 weeks, and 12 weeks (treatment cessation) after the baseline visit (Visit 2). No other erectogenic aids are allowed during the 12-week ( $\pm 1$  week) treatment period. Patients will be managed using standard of care but will attend the site for follow-up evaluation at 12-weeks ( $\pm 1$  week). Study assessments will include: IIEF, SEAR, EPIC and climacturia questionnaires, stretched flaccid penile length, urinary incontinence analysis, prostate-specific antigen (PSA) assessments, and use of other erectogenic aids specifically penile prosthesis placement.

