##### ***Male subject inclusion criteria***

1. Men who underwent bilateral nerve-sparing radical prostatectomy between 18 and 48 months prior to study commencement
2. Age 40 – 70 at the time of screening.
3. Diagnosed with prostate cancer:
  - a. PSA < 20 ng/ml
  - b. Gleason score <= 8
  - c. PCa stage <= T3a
4. Normal pre-radical prostatectomy erectile function (EPIC-CP question 8 score of 0 [firm enough for intercourse] or IIEF > 26)
5. Baseline erectile dysfunction at time of screening (despite use of erectogenic aids of any kind) and at enrolment following washout (IIEF-EF domain <= 25)
6. Sexually active, in a stable heterosexual relationship for at least 6 months prior to screening
7. Female partner meets their respective inclusion and exclusion criteria
8. Able to understand and complete patient questionnaires
9. Serum PSA undetectable (no evidence of disease recurrence)
10. Willing and able to provide written consent to participate in the study (note: both the patient and his female partner must provide written consent to participate before any study related procedure is undertaken)
11. Willing to refrain from the use of other erectogenic devices and pharmaceutical interventions during the washout and 12-week treatment periods.

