#### **End of Study Definition**

The study ends once the last patient enrolled in the study has undergone Visit 6 or lost to follow-up.

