### ***Stopping / discontinuation rules***

Completion of trial is defined as the point at which the last patient enrolled in the study has completed the visit 6 (week 13) follow-up phone call visit or withdrawn from the study.

Although unlikely to occur, the study may also be terminated early if recurrent serious protocol deviations are reported, and/or the study team is unable to continue (e.g. manpower or financial issues). In this case, a report will be filed with the IRB within 1 month, and all treated patients

will continue to be followed up until follow-up visit (Visit 6) if possible and undertake the assessments scheduled for each visit.

The final clinical study report will document the reasons for trial discontinuation if it occurs.

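### An injection or implant outcome is listed at 12 months, but no contact is planned after the week-13 call; as a lesser point, the visit text and the schedule disagree on a week-12 PSA sample

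*Combined protocol and SAP*

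**What the plan says.** **Use of injection or implant.** Section 9 (Analysis of Secondary and Safety Endpoints) lists "Proportion of patients on penile injection therapy or penile implant at 12 months follow-up". It gives no origin for the 12 months. Section 3 names among the study assessments "prostate-specific antigen (PSA) assessments, and use of other erectogenic aids specifically penile prosthesis placement". The outcome is not among the Section 2 objectives.

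**End of follow-up.** The visit text describes the last contact as "Follow-up Visit 6 (phone-7 day post-study treatment", with a window of 2 days either side. The Schedule of Assessments puts it at week 13, give or take a week. At that call, "Usage of erectogenic aids will also be recorded". The End of Study Definition reads: "The study ends once the last patient enrolled in the study has undergone Visit 6 or lost to follow-up". The stopping rules in Section 10 likewise define completion as the point when the last man has "completed the visit 6 (week 13) follow-up phone call visit or withdrawn from the study".

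**Ban on other aids.** Section 3 states: "No other erectogenic aids are allowed during the 12-week" treatment period. Male inclusion criterion 11 covers washout and treatment. The Concomitant Treatment section extends the ban to the whole of participation, and has the site ask about concomitant treatment at each visit.

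**PSA.** Section 9 also lists PSA evidence of biochemical recurrence, with no time point or threshold. The Visit 5 text has a PSA sample taken. The schedule marks PSA at screening only, and its footnote 8 deals only with the eligibility sample. The Withdrawal Criteria define recurrence as PSA of at least 0.2 ng/ml.

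**The concern.** A listed endpoint needs a planned observation at its time point. For the 12-month line there is none. This differs from dropout: the data are absent for every man by design, and Section 9 rules out imputation. At reporting, the endpoint would have to be dropped after the fact or filled from whatever later information happened to be available, which would be unplanned and selective.

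The PSA line has a milder form of the same problem. Whether it has any post-baseline study value depends on whether staff follow the visit text or the schedule. Even with a sample, the line does not say what is to be estimated.

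**Working it through.** The plan gives no figure to reproduce for this point, and Section 9 states that there is no formal sample size calculation. The check sets the endpoint list against the planned contacts.

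**Inputs**
- 12 months = 365.25 / 7 = 52.2 weeks.
- Visit 6 by the schedule: week 13 ± 1, so week 12 to 14 after Day 1.
- Visit 6 by the visit text: 7 ± 2 days after treatment. Taking treatment to end at Visit 5 (week 12 ± 1), this is week 11 + 5/7 = 11.7 to week 13 + 9/7 = 14.3.
- Visit 1: 4 or 5 weeks before Day 1 (schedule).
- Entry: "Men who underwent bilateral nerve-sparing radical prostatectomy between 18 and 48 months prior to study commencement" (male inclusion criterion 1).
- About 20 men (Section 9).

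**Gap between the last planned contact and month 12**

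| 12 months counted from | Calculation | Result |
|---|---|---|
| Day 1, schedule timing | 52.2 − 14 to 52.2 − 12 | 38.2 to 40.2 weeks short |
| Day 1, visit-text timing | 52.2 − 14.3 to 52.2 − 11.7 | 37.9 to 40.5 weeks short |
| End of treatment | 52.2 − 9/7 to 52.2 − 5/7 | 50.9 to 51.5 weeks short |
| Visit 1 (Visit 6 is 16 to 19 weeks later) | 52.2 − 19 to 52.2 − 16 | 33.2 to 36.2 weeks short |
| Surgery | 18 − 12 to 48 − 12 | passed 6 to 36 months before entry |

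No origin gives a 12-month time point at which a man is under planned observation in the study. Planned observations are 0 of about 20.

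**If 12 weeks was meant.** Neighbouring lines in the Section 9 list do use 12 weeks. At week 12, however, injections and implants are barred under all three statements of the ban. The proportion would be near zero by design, and any user would be a protocol deviation.

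**Other possible sources.** Record review is described only for recruitment (Section 5). After the final visit, unresolved adverse events are followed medically but not entered in the eCRF, and the manufacturer may ask for details of ongoing events. Neither supplies injection or implant use for all men.

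**PSA, side by side**

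| Text | Post-baseline study PSA |
|---|---|
| Visit 5 description | one sample, week 12 ± 1 |
| Schedule, PSA row and footnote 8 | none |
| Visit 6 description | none; monitoring left to the primary urologist |

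The Section 9 line therefore has a value for every man attending Visit 5, or for none.

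**Precision if data were collected** (exact Clopper-Pearson 95% intervals). With 0 of 20 recurrences, the upper limit is 1 − 0.025^(1/20) = 16.8%. For injection or implant use, an assumed 5 of 20 gives 8.7% to 49.1%, and an assumed 10 of 20 gives 27.2% to 72.8%. These two counts are illustrations only.

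**The case against.** This is an exploratory, single-arm pilot, the 12-month line serves no stated objective, and the primary analysis does not depend on it. That is right, and it limits the weight of the point, but the endpoint still has no data.

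It can also be said that the study ends with the last man's Visit 6, so early entrants might pass 12 months while it is still open. No contact is planned for them then, so this supplies nothing.

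On PSA, the conflict is an explicit instruction against an unmarked cell, and the Visit 6 referral to the urologist does not contradict a week-12 sample. Both are fair, and they are why this part is secondary. The schedule was also split in text extraction. Even so, the PSA row sits in the part with the full visit columns, and footnote 8 mentions only eligibility samples, so a lost mark is unlikely.

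Three stronger readings are tempting, and the documents do not support them:
- *That Visit 6 is the only follow-up record of aid use.* Concomitant treatment is asked about at each visit. Visit 6 is only the last record.
- *That the absence of PSA testing between baseline and Visit 5 is itself a defect.* Men enter with undetectable PSA, Section 7 anticipates no recurrence risk from the gel, and nothing requires interim testing.
- *That the Visit 5 sample is plainly left over and should go.* The Version 5.0 log entry describes removing a repeat PSA after treatment, but it is a change log. Section 3, the Visit 5 text, Section 9 and the withdrawal rule fit keeping the sample at least as well.

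**Conclusion.** The point holds and should be fixed. The 12-month injection or implant endpoint has planned data for 0 of about 20 men. The shortfall is 38 to 40 weeks from Day 1 on the schedule's timing, and no alternative origin or 12-week reading yields a usable value. This rests on the absence of any later call or record review in the protocol, and on Visit 6 taking place within its stated window.

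The PSA mismatch is real but lesser. The recurrence assessment has week-12 data under the visit text and no post-baseline study data under the schedule. The documents do not settle which was intended.

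A reader should not infer that the efficacy conclusions are at risk: the primary IIEF-EF comparison at 12 weeks uses neither item.

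**What to change.** **12-month line.** The simplest change is to delete it from Section 9 and report use of other aids, including prosthesis placement, descriptively as concomitant treatment through Visit 6. This costs wording only, and the long-term outcome is given up.

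If the outcome is wanted:
- Add one call 12 months after Visit 2 and state that origin in Section 9. A record review is possible instead, but would be incomplete for men treated elsewhere.
- Extend the schedule, the End of Study Definition and the stopping rules to match.
- Limit the ban in the Concomitant Treatment section to washout and treatment; otherwise longer participation bars the very aids being counted.
- State that the 12-week efficacy analysis does not wait for the call, since Section 9 now ties it to completion of all follow-up visits.

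This costs about 20 calls and keeps the study open 38 to 40 weeks longer. Men who withdraw from the study would have no value, because Section 10 stops new data collection then, and the estimate would be imprecise, as the intervals above show.

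**PSA.** The sponsor should say which text is intended and make the other agree:
- *Sample kept:* mark PSA at Visit 5 in the schedule and define the endpoint as the proportion with PSA of at least 0.2 ng/ml at week 12 among men sampled. The cost is one draw at a planned on-site visit.
- *No post-treatment study PSA:* remove the Visit 5 draw and the Section 9 line, and state that the withdrawal rule acts on standard-of-care results reported to the site. This is wording only, and the study then has no PSA of its own after treatment.
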